10. DEMOGRAPHIC AND OTHER BASELINE CHARACTERISTICS

Analyses will be carried out on the ITT population, in a descriptive manner, using appropriate statistics as described in Section 6.1. Results will be provided on the pooled data across the two arms and by arm.

If the ITT population and the PP population differ by more than 10% (that is, if more than 10% of patients in the ITT population are finally excluded from the PP population), the analyses will be further carried out on the PP population.

These results will also be presented in the appendix for patients of the optional sub-study who had a biopsy at V1 and for patients of the optional sub-study who had a biopsy at V9. These results will be provided based on the pooled data across the two arms and by arm.

Number and percentage of patients with and without each eligibility criterion will be provided on the pooled data across the two arms and by arm.

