14.2. ADVERSE EVENTS

Analysis will be based on data recorded on "Adverse event" eCRF forms.

All expected or unexpected serious adverse events (AE), adverse event of special interest (AESI) (Conjunctivitis), and all unexpected non-serious adverse events, occurring from the date of consent signature, during the study duration, have been collected and documented on an AE form after coding according to the standardized MedDRA medical dictionary.

Thus, the incidences per group of each type of AE according to the Preferred Term (PT) will be presented and organized by System-Organ Class (SOC). If a subject had multiple AEs of the same PT, only one will be counted, so the denominator will be the number of treated subjects and the numerator the number of subjects experiencing at least one AE of that type. The same descriptive table will be presented for serious AEs and for AEs whose causality to the study or treatment is not excluded. Percentages of subjects with at least one AE, at least one serious AE, and at least one AE for which causality to the study or treatment is not excluded will be calculated with exact 95% CI.

A listing of all serious AEs and AESIs will be produced based on the treatment actually received and will contain the following informations:

- Subject and center identifier
- Date of first study treatment administration
- Date of last study treatment administration
- Date and time of the start of the AE
- Date and time of the end of the AE (or mention of the persistence of the adverse event)
- Description of the event ("Reported Term" and "Preferred Term")
- Severity, intensity
- Causality to the trial or trial treatment
- Action on the trial treatment
- Other action and evolution

The following will be presented by arm (Placebo / Dupilumab):

- The incidence of AE and AESIs based on their causality and severity
- The incidence of AE and AESIs leading to the cessation of trial treatment
- AEs and AESIs occurring between the consent signature and the first administration of treatment

In addition to these safety analyses, the percentage of patients reporting injection site reactions will also be presented overall and by group with exact 95% CI together.

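### Related adverse events pool study and treatment causality, so the summary percentage can include procedure events; a treatment-only line would be a cheap improvement

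*SAP*

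**What the plan says.** SAP section 14.2 plans adverse-event incidence by arm, by preferred term within system organ class, with treated subjects as the denominator. It then repeats this table for serious events and "for AEs whose causality to the study or treatment is not excluded". The patient-level summary uses the same class: the percentage with "at least one AE for which causality to the study or treatment is not excluded will be calculated with exact 95% CI". In the listing of serious events and events of special interest, causality is one item: "Causality to the trial or trial treatment". A further by-arm output is "The incidence of AE and AESIs based on their causality and severity", with no definition of the causality categories.

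The same section collects serious events, events of special interest (conjunctivitis) and unexpected non-serious events, all from the signing of consent. It presents events between consent and first dose on their own, and gives injection-site reactions their own percentage with exact CI. The opening of section 14 makes safety descriptive, without tests.

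Study procedures appear elsewhere. Section 10 refers to "patients of the optional sub-study who had a biopsy at V1 and for patients of the optional sub-study who had a biopsy at V9", and section 11 mentions the same sub-study. Sections 10.3 and 13.2.8 describe blood tests at inclusion, at V1 (IgE) and at V9.

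**The concern.** The safety objective in section 4 compares dupilumab with placebo. A reader will take the related-event percentage as the rate of suspected drug reactions, but as defined it is not quite that. An event caused by a biopsy or a blood draw is related to the study whatever the patient was injected with, and it counts.

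Timing adds to this. Section 6.3.10 sets date rules for deriving treatment-emergence, but section 14.2 does not restrict the related-event table or percentage to treatment-emergent events. A screening-procedure event before the first dose can therefore enter the related class in a patient who is later treated, although the drug cannot have caused it. The separate display of pre-dose events does not remove them from that class.

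If procedure events are about equally common in both arms, they raise both percentages and bring them closer together. At stake is how clearly a descriptive safety summary reads. The primary endpoint is not affected.

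**Working it through.** **1. What the SAP supplies.** It gives no figure for related events, sub-study size or procedure-event rate, so there is no figure of the plan's own on this point to reproduce. Only arm size can be taken from it. Section 5.3 has 84 evaluable patients and 10% non-evaluable: 84 / (1 - 0.10) = 93.3, rounded up to 94, or 47 per arm at 1:1. This agrees with the SAP.

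**2. Which outputs the pooling reaches.**
- *At-least-one percentage:* fully affected, because any study-related event counts.
- *Preferred-term table:* a term specific to biopsy has its own row. Only terms that both causes can produce are mixed.
- *Incidence by causality and severity:* it could separate the causes, but its categories are undefined.
- *All-event and serious-event tables, injection-site reactions:* not affected, since they do not use the merged class.

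**3. Formula for the percentage.** Let d be the proportion with a treatment-related event and q the proportion with a recorded procedure event. Assume q is equal in both arms and independent of d. The merged percentage is

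p = 1 - (1 - d)(1 - q).

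Each arm's percentage rises by q(1 - d). The risk difference becomes (d1 - d0)(1 - q), so it shrinks by the factor 1 - q.

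**4. Results.** All rates are assumptions, dupilumab v placebo.

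| True rates | q | Merged rates | Risk difference (points) | Risk ratio |
|---|---|---|---|---|
| 30% v 15% | 0 | 30.0% v 15.0% | 15.0 | 2.00 |
| | 2% | 31.4% v 16.7% | 14.7 | 1.88 |
| | 5% | 33.5% v 19.3% | 14.3 | 1.74 |
| | 10% | 37.0% v 23.5% | 13.5 | 1.57 |
| | 20% | 44.0% v 32.0% | 12.0 | 1.38 |
| 20% v 10% | 0 | 20.0% v 10.0% | 10.0 | 2.00 |
| | 2% | 21.6% v 11.8% | 9.8 | 1.83 |
| | 5% | 24.0% v 14.5% | 9.5 | 1.66 |
| | 10% | 28.0% v 19.0% | 9.0 | 1.47 |
| | 20% | 36.0% v 28.0% | 8.0 | 1.29 |

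**5. A case built from biopsy uptake.** Assume that 30% join the sub-study and 20% of them have a recorded event: q = 0.30 × 0.20 = 0.06. With true rates of 10% v 4%, the merged rates are 1 - 0.90 × 0.94 = 15.4% and 1 - 0.96 × 0.94 = 9.8%. The ratio falls from 2.5 to 1.6, but the difference only from 6.0 to 6.0 × 0.94 = 5.6 points.

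**6. Against the precision available.** For 5 of 47 patients (10.6%), the exact 95% interval runs from 3.5% to 23.1%. A 0.4-point change in the difference cannot be seen against that. What changes more is the level in each arm: at q = 5% and 20% v 10%, the percentages rise by 4.0 and 4.5 points.

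**The case against.** A good deal stands on the other side.

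- **Collection rule.** Expected non-serious events are outside the stated collection. Routine soreness or bruising after a biopsy or blood draw may count as expected and never reach the form. What counts as expected is not shown in the SAP. This stands, and it argues for the low end of the range for q.
- **Term-level rows.** A reader might infer that the whole related-event table mixes drug and procedure reactions. The SAP does not support that: terms specific to biopsy are visible on their own rows. What remains is the summary percentage and the shared terms.
- **The output by causality and severity.** A reader might infer that no planned output separates treatment causality. This cannot be asserted, because that output might do so. But its categories are undefined and the only causality item described is the merged one, so the separation is possible, not specified.
- **Choice of scale.** The risk ratio makes the dilution look large, but the SAP plans no risk ratio for adverse events, only percentages with exact intervals. This stands.
- **A broad class is conservative.** It misses no possibly related event and contradicts nothing in the SAP. That is a reason to keep it as a secondary line. It does not make it the best headline measure of drug reactions.

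**Conclusion.** The point holds as a minor improvement. The merged definition is explicit, no output is expressly limited to treatment-related events, and the at-least-one percentage can include procedure and pre-dose events that the drug did not cause.

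The likely effect is a modest dilution. In the two scenarios tabulated, the risk difference falls by 0.2 to 0.8 points if 2-5% of patients per arm have a recorded procedure event, and by 1.0 to 3.0 points if 10-20% do. These results rest on assumed rates, on equal procedure-event rates in the arms, and on independence from drug reactions.

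A reader might go further and infer that the pooling biases the safety comparison, or that uneven biopsy uptake creates or hides a difference. The SAP does not support this. Chance imbalance in an optional procedure is possible, but no direction is shown. Safety is descriptive and no test rests on the percentage. Severity is low.

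**What to change.** In section 14.2:

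1. Define the causality categories, and apply them also to the incidence by causality and severity.
2. Give the related-event table, and the at-least-one percentage with its exact 95% CI, for events whose causality to the study treatment (dupilumab or placebo) is not excluded.
3. Show events related only to study procedures, including biopsy, separately.
4. Keep the merged study-or-treatment class as a secondary line.

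The cost is SAP wording and one extra table. If the adverse-event form holds a single merged causality field, the events flagged as related need a blinded medical review before unblinding; reclassifying them afterwards would be open to bias.
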